2.1 Primary objective

To assess the feasibility of deploying the iLet bionic pancreas system in the insulin-only configuration to

pump-naïve MDI users with type 1 diabetes, in the setting of being recruited from community-based primary care practices and being trained and managed by primary care providers (PC group), and in pump- and CGM-experienced (sensor-augmented pump or hybrid closed-loop) users with type 1 diabetes recruited from, trained, and managed by an academic endocrinology practice (EN group). In both practice settings, the exclusive use of telehealth (TH) visits will be assessed, as will use of in-person (IP) visits.

We will enroll 40 adult volunteers (18-85 years old) with type 1 diabetes, 20 who are insulin pump naïve MDI users enrolled from community primary care practices by University of Colorado Family Medicine (PC group) and 20 who are technology-savvy sensor-augmented pump or hybrid closed-loop users enrolled by the Massachusetts General Hospital Diabetes Clinical Research Center (EN group). Ten of the participants at each center will be trained and managed throughout the trial using in-person visits (PC-IP and EN-IP groups) and the other ten from each center will be trained and managed throughout the trial exclusively via telehealth visits (PC-TH and EN-TH groups). The 40 participants will be evenly divided into these four groups, but not by randomization. Participants will be assigned to either the in-person or telehealth arm based on the participant's preference, the participant's location, and the discretion of the investigator. Subjects in all four groups will each participate, in random order, in one 14-day study arm under their own usual care (UC arm) and one 14-day study arm under the insulin-only configuration of the iLet bionic pancreas (iLet arm).

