2.2 Secondary objectives

1. To obtain preliminary data on the quality of glycemic control among the PC and EN groups, with separate analyses in the IP and TH sub-groups, and in the UC and iLet arms within those groups, which will be used to power a larger study with a glycemic control metric as the primary outcome. Our hypotheses are that glycemic control, with key outcomes being group mean CGM glucose, the group mean time with CGM glucose less than 54 mg/dl, and the group mean time with CGM glucose in the 70–180 mg/dl range, will be similar in the PC-IP group and the EN-IP group, and in the PC-TH group and the EN-TH group in the iLet arm. Additionally, we hypothesize that glycemic control will be similar in the PC-TH group and the PC-IP group, and in the EN-TH group and the EN-IP group in the iLet arm. Further, we hypothesize that there will be a larger difference in glycemic control metrics between the UC arms versus the iLet arm in the PC group than there will be in the EN group.
2. To assess the impact of the insulin-only configuration of the iLet bionic pancreas system on psychosocial outcomes (including quality of life, fear of hypoglycemia, and diabetes distress) among study participants. Secondary analyses will be conducted between the telehealth and in-

person arm, the EN and PC groups, and the iLet and UC arms.

3 Participant Selection

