5.1 Study Design

This study will assess delivery of the insulin-only iLet bionic pancreas by primary care providers and endocrinologists, as well as delivery of the iLet bionic pancreas via in-person training and support vs telehealth training and support. It will employ a two-center, random-order, two-arm cross-over trial design in a home-use setting in 40 adult participants (18-85 years of age) with type 1 diabetes. This number is based on 10 participants per arm, per site, which has been successfully implemented in previous iLet studies and which has yielded highly significant results in those studies. The two centers will be community-based primary care and academic medical center-based endocrinology. Study participants will be managed by appropriate site-specific study team clinicians: endocrinology providers at MGH, or primary care providers at CU.

The two 14-day study arms will occur in a random-order cross-over design. One arm will involve using the insulin-only iLet bionic pancreas and the other arm will involve insulin delivery via the participants' usual care (multiple daily injections or insulin pump, depending on the study site). Half of the participants will receive care via in-person visits, and the other half will receive care exclusively via telehealth visits. This will result in four study cohorts overall [endocrinology in-person (EN-IP), endocrinology telehealth (EN-TH), primary care in-person (PC-IP), primary care telehealth (PC-TH)].

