6.6 Sample Size Determination

No formal statistical power or sample size calculations have been done for this study. This study is primarily intended to be a feasibility trial to verify that the iLet can be managed by both primary care physicians, endocrinologists, and delivered through telehealth.

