6.7 Statistical Analyses

An intention-to-treat analysis will be performed. Descriptive statistics will be used to summarize patient characteristics and assessments. We will estimate the percentage of participants who have a mean sensor glucose <183 mg/dl in the iLet arms of all four groups (PC-IP, PC-TH, EN-IP, EN-TH), along with confidence intervals using the Clopper-Pearson method. The hypothesis is that there is no difference in the percentage of each group that meet this metric.

The primary analysis of the designated endpoints will be calculated on an intention-to-treat basis. In cases where an arm was not completed, we will use the available data from that arm in the data analysis. We will calculate percentages, means, standard deviations (and medians and interquartile ranges as appropriate), and ranges in descriptive analyses. Unless otherwise specified, continuous data will be summarized by presenting the number of non-missing observations, mean and standard deviation (SD) or median, minimum, and maximum. Categorical data will be summarized by presenting the number of patients and percentage for each category. We will use the t-test for comparisons of means for normally distributed outcomes and the Mann-Whitney U test for comparisons of medians on non-normally distributed outcomes between groups (PC-IP, PC-TH, EN-IP, EN-TH). We will use the paired t-test for comparison of means for normally distributed outcomes and the Wilcoxon Signed Rank test for comparisons of medians on non-normally distributed outcomes when comparing between iLet and usual care within groups. There will be no adjustments for multiple comparisons.

We may, in exploratory analyses, also stratify subjects for secondary analyses of the pre-specified endpoints by the following characteristics: sex, age, usual care insulin total daily dose, body mass index, baseline A1c, and use of CGM in usual care.

P-values can be displayed to aid interpretation, not for inference. Tables, figures and listings of all primary, secondary and safety endpoints will be created.

Data from periods when the bionic pancreas was not in use will be included, if available (Dexcom CGM data may not be available in some failure modes).

All questionnaire data (including quality of life data) for patients who have completed a minimum of 4 days with a device will be included. Results will be compared by Wilcoxon signed-rank test.

6.7.1 *Safety Analyses*

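### Section 6.7 names no pooled glycemic comparison for the setting, visit-mode and UC-iLet hypotheses; adding averaged 2x2 effects beside the cell contrasts would answer the first two with intervals about 32% narrower

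*Combined protocol and SAP*

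**What the plan says.** The design crosses care setting (PC or EN) with visit mode (IP or TH). Section 2.1 states: "Ten of the participants at each center will be trained and managed throughout the trial using in-person visits (PC-IP and EN-IP groups". The other ten at each center are seen by telehealth. Allocation to cells is by preference, location and investigator discretion: "The 40 participants will be evenly divided into these four groups, but not by randomization". Section 5.1 gives precedent as the basis for the cell size ("This number is based on 10 participants per arm, per site"), and section 6.6 adds: "No formal statistical power or sample size calculations have been done for this study".

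The glycemic hypotheses are posed at two levels.

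- **Factor level.** Section 2.1 expects similar iLet control across the two settings and across the two visit modes. Section 2.2 expects a larger usual care to iLet difference in PC than in EN.
- **Cell level.** Section 2.2 also says that glycemic control "will be similar in the PC-IP group and the EN-IP group, and in the PC-TH group and the EN-TH group in the iLet arm", and that "glycemic control will be similar in the PC-TH group and the PC-IP group, and in the EN-TH group and the EN-IP group".

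For analysis, section 6.7 says: "We will use the t-test for comparisons of means for normally distributed outcomes". It gives the Mann-Whitney test for medians "on non-normally distributed outcomes between groups (PC-IP, PC-TH, EN-IP, EN-TH". Paired tests compare iLet with usual care within groups. No regression, analysis of variance or pooled comparison is named for a glycemic outcome.

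**The concern.** The factor-level hypotheses have no matching analysis. Four 10 v 10 contrasts address setting twice and mode twice, each within one stratum, and nothing says how to combine each pair into a statement about primary care or telehealth overall. The third hypothesis compares a within-person difference between PC and EN. Neither the paired tests within groups nor the tests among four cells do that.

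What is at stake is precision and pre-specification. Section 2.2 says that these data will be used to power a larger study, and section 6.7 offers p-values only as an aid to interpretation, so interval width is what a reader has for judging similarity. For scale, usual care and iLet means differed by 8 mg/dl in the adult bridging study (163 v 155, section 12.1.8). If pooling is decided only after the data are seen, it also becomes a data-driven choice.

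**Working it through.** The plan states no power or precision figure, so there is none to reproduce. The layout is consistent: 4 cells x 10 = 40.

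**Inputs**

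- Cell size 10 (sections 2.1 and 5.1).
- Two-sided 95% intervals. This is an assumption, since section 6.7 names no level.
- SD of individual mean CGM glucose on the insulin-only device: 9 to 17 mg/dl. This is the range in the protocol's adult insulin-only results at targets of 110 to 130 mg/dl (Tables 1 and 2): 9 in the Stanford study, 11 and 13 in the monitoring study, 13 in the bridging study with lispro or aspart, and 15, 15 and 17 in the set point study. That these carry over to the present cells is an assumption. The SD cancels in the ratio of widths.
- Common variance across cells.

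**Half-widths in SD units**

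1. One cell contrast, 10 v 10, as planned: t(0.975, 18) x sqrt(2/10) = 2.101 x 0.4472 = 0.940.
2. Averaged setting or mode effect from the model with interaction: t(0.975, 36) x sqrt(2/20) = 2.028 x 0.3162 = 0.641.
3. One cell contrast taken from the same model, using the pooled error variance: 2.028 x 0.4472 = 0.907.
4. Interaction, a difference of two cell contrasts: 2.028 x sqrt(4/10) = 2.028 x 0.6325 = 1.283.

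**In mg/dl, mean CGM glucose**

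| Quantity | SD 9 | SD 13 | SD 17 |
|---|---|---|---|
| Cell contrast, planned | 8.5 | 12.2 | 16.0 |
| Averaged effect | 5.8 | 8.3 | 10.9 |
| Cell contrast, pooled variance | 8.2 | 11.8 | 15.4 |
| Interaction | 11.5 | 16.7 | 21.8 |

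**Reading the results**

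- Averaged effect against planned contrast: 0.641/0.940 = 0.68, so 32% narrower. The standard error alone gives 1 - sqrt(0.5) = 29.3%; the rest comes from degrees of freedom. With 9 or 8 completers per cell the gain is 32.1% or 32.5%.
- Within-stratum contrast: 0.907/0.940 = 0.965, so 3.5% narrower.
- A simulation of 20,000 trials at SD 13 gave mean half-widths of 12.0 and 8.3 mg/dl, with about 95% coverage of the averaged effect. With a true interaction of 10 mg/dl, the averaged interval covered the effect in a single stratum only 78% of the time.
- Third hypothesis: a setting term on the within-person difference has the same half-width of 0.641, in units of the SD of that difference. The documents do not give that SD, so no mg/dl figure is offered.

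**The case against.** The best defence is that the cell-level questions are deliberate. Section 8 lists three separate untested care models, the protocol summary brings in endocrinology as a comparison, section 2.1 sets the 183 mg/dl target for each of the four groups, and section 2.2 writes the contrasts within strata. The trial is a feasibility study, and section 2.1 says that its primary outcome is not a comparison of mean glucose between groups. The larger trial mainly needs means and SDs, which section 6.7 already reports.

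Much of this stands. It is a good reason to keep the four contrasts, and it keeps the stakes modest. It does not supply an analysis for the factor-level hypotheses.

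Three stronger readings are tempting, and the documents do not support them.

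- **That each contrast in section 2.2 could be estimated a third more precisely from all 40 participants.** The telehealth participants inform the PC-IP v EN-IP mean difference only if the setting effect is assumed equal in both modes. Without that assumption they contribute only to the error variance, hence the 3.5%.
- **That the plan never looks across the two halves.** Section 2.2 frames its first objective around the PC and EN groups, its third hypothesis is 20 v 20, and its psychosocial objective names both factor comparisons. The gap is that section 6.7 names no pooled glycemic test.
- **That a 2x2 model makes this a factorial experiment.** Cells are not randomized. Visit mode follows preference, location and discretion, and setting coincides with site and with injection v pump and CGM background. The model narrows intervals around confounded differences, and the planned t-tests share that limitation.

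**Conclusion.** The point holds as a gap between the hypotheses and the named analyses, with an inexpensive remedy. It is not an error in the planned tests. The 32% narrowing is independent of the SD and rests on balanced cells, common variance and an interest in effects averaged over the other factor. It does not carry over to the pre-stated within-stratum contrasts.

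Forty participants cannot verify that the effects are additive: at SD 13 the interaction interval is about +/-16.7 mg/dl, wider than that of any cell contrast. The averaged effect must therefore be read as an average. At the same SD its half-width of 8.3 mg/dl is only about the size of the 8 mg/dl benchmark, so it improves the answer on similarity without settling it. The half-widths concern means and do not apply to time below 54 mg/dl, which is likely to be skewed.

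**What to change.** Add the following to section 6.7 and keep the four cell contrasts as stated.

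- **Mean CGM glucose and time in 70-180 mg/dl, iLet arm:** a linear model with setting, visit mode and their interaction. Report the average setting effect, the average mode effect and the interaction, each with a 95% CI, beside the cell means.
- **Third hypothesis:** for the same outcomes, model the within-person usual care to iLet difference with a setting term and visit mode. Report the setting effect with a 95% CI.
- **Time below 54 mg/dl:** a stratified rank test (van Elteren), comparing settings stratified by mode and modes stratified by setting. Because this gives a test and no interval, add a bootstrap interval.
- **Limits to state:** the interaction is estimated too imprecisely to confirm additivity, and the model does not remove confounding by non-random visit mode, site or prior treatment.

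The cost is a paragraph of SAP wording, with no new participants or data. The price in interpretation is that an averaged effect is harder to read if the interaction looks large, which is why the interaction and cell results belong in the same table. The text should be fixed before the data are examined.

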1.3.2 Fully Integrated iLet® BP System (Beta Bionics)

The iLet® Bionic Pancreas System (iLet) is a wearable device that integrates CGM technology via its built-in Bluetooth radio, two independent motor–drivetrain pumping mechanisms, which independently deliver insulin and glucagon from glass cartridges, and embedded software that includes our adaptive control algorithms. The iLet is compatible with three insulin analog formulations (insulin lispro, Lilly; insulin aspart and Fiasp, Novo Nordisk) and one glucagon analog (dasiglucagon, Zealand Pharma). The

iLet also includes a touchscreen display that provides a custom graphical user interface. In addition to the iLet ready-to-fill glass insulin cartridge and the prefilled glass dasiglucagon cartridge, the iLet uses separate insulin and glucagon administration sets, each with a proprietary connector to connect to its respective. Figure 1 illustrates the iLet's system components and a summary of its virtues and capabilities.

The iLet® Bionic Pancreas

Figure 1 Illustration of the iLet (Beta Bionics, Inc.) system components and capabilities. It is interoperable with one of two CGM devices and is compatible with three insulin analog formulations and one glucagon analog.

Additionally, the iLet continually provides daily insulin dosing recommendations (for temporary self-management, should the iLet become temporarily unavailable, e.g. broken or lost), specifically (i) four 6-h basal rates for pump therapy or a 24-h long-acting basal dose for MDI therapy, (ii) a “correction factor” for insulin doses, and (iii) prandial insulin doses for the three main meals of the day. These are direction outcome of the autonomous learning capability of the iLet’s three insulin controllers (basal, correction, and meal-dose controllers).

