5.5.3 Randomization of Study Arm Sequence

Participants will be recruited specifically into the in-person or telehealth cohorts, based on their circumstances. Once the participant has been enrolled and eligibility has been established, participants within each of these cohorts will be randomized to one of two possible study arm sequences.

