5.6.1.2.2 UC arm

- No modifications will be made to dosing regimens for participants in the usual care arm.
- Study staff will confirm the participant is wearing the study CGM, and answer any questions the participant may have about the CGM. They will remind the participant to replace the study CGM after 10 days.

5.6.1.3 Crossover Visit (Visit 5):

- At the end of the first study period (Day 14 [+2]), participants will return to the clinic and answer the post questionnaires for the study arm.
- A urine pregnancy test will be performed in participants of child-bearing potential. If the test is positive, the participant will be informed of the result and the next planned study arm will not proceed. The date of the last menstrual period will also be documented.
- Any changes to medications or medical history and any adverse events that may have occurred since the last study visit will be documented.

- All study devices applicable to the arm just completed will be downloaded
 - BP arm: iLet and study glucometer and ketone meter
 - UC arm: Dexcom G6 and study glucometer
- Participants will repeat psychosocial questionnaires (including quality of life, fear of hypoglycemia, diabetes distress).
 - Participants coming off of the BP arm will be asked to complete the Bionic Pancreas User Opinion Survey
- Participants will then start over with Day 1 procedures for the arm they are randomized to next. This may occur immediately, or within 14 days after the completion of the first arm.
 - If the participant is switching from usual care to bionic pancreas:
 - If using an insulin pump (EN group), their own insulin infusion pump will be stopped and disconnected if applicable, and its infusion set will be removed
 - If using MDI therapy (PC group), they will be instructed not to take any additional insulin injections once the bionic pancreas is started, unless instructed to do so by study staff
 - If the participant is switching from bionic pancreas to usual care, a provider (MD or NP) will review the last several hours of insulin dosing and assist the participant in resuming their usual care.
 - For participants whose usual care is MDI therapy:
 - If normal long-acting dose time is MORNING:
 - Morning study visit – take full dose at visit, take next day dose at usual time
 - Afternoon study visit – three quarters of normal dose at visit, take next day dose at usual time
 - If normal long-acting dose time is EVENING:

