- A urine pregnancy test will be performed in participants of child-bearing potential. Participants will be instructed to complete the pregnancy test during the virtual visit and to show result to study staff. If the test is positive, the participant will be informed of the result and the next planned study arm will not proceed. The date of the last menstrual period will also be

documented.

- They will start over with Day 1 procedures for the arm they are randomized to next. This may occur on the same day, or within 14 days of the final visit of the first arm.
 - If the participant is switching from usual care to bionic pancreas:
 - If using an insulin pump (EN group), their own insulin infusion pump will be stopped and disconnected if applicable, and its infusion set will be removed.
 - If using MDI therapy (PC group), they will be instructed not to take any basal insulin starting the morning of this study visit, and no additional insulin injections once the bionic pancreas is started, unless instructed to do so by study staff
 - If the participant is switching from bionic pancreas to usual care, a provider (MD or NP) will review the last several hours of insulin dosing and assist the participant in resuming their usual care.
 - For participants whose usual care is MDI therapy:
 - If normal long-acting dose time is MORNING:
 - Morning study visit – take full dose at visit, take next day dose at usual time
 - Afternoon study visit – three quarters of normal dose at visit, take next day dose at usual time
 - If normal long-acting dose time is EVENING:
 - Morning study visit – take half of full dose at visit (acts as loading dose), take full dose at normal time that same evening
 - Afternoon study visit – take one fourth of full dose at visit (acts as loading dose), take full dose at normal time that same evening
- Investigators may use a different approach according to their judgment.
- Participants will repeat psychosocial questionnaires (including quality of life, fear of hypoglycemia, diabetes distress).
 - Participants coming off of the BP arm will be asked to complete the Bionic Pancreas User Opinion Survey

5.6.2.4 Final Visit (Visit 8):

- The body weight of the participant will be documented using the scale provided.
- Any changes to medications or medical history and any adverse events that may have occurred since the last study visit will be documented.

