5.7.1 Policies for the Usual Care Arm

- Participants may be contacted between visits if needed, per the discretion of either the participant, a healthcare provider, or a member of the study team.
- The UC arm will continue its pre-study diabetes management, including approach to insulin delivery and management. Diabetes management will be handled by the participant's usual diabetes health care provider. *No adjustments to the diabetes care plan will be made by the study team.*

- Participants in the endocrinology (EN) cohort using FDA-approved devices as part of their pre-study usual care, such as a CGM system, insulin pump, or closed-loop system can continue use of their personal devices during the study period. Use of devices that are not FDA-approved is prohibited.

5.7.2 *Policies for the Bionic Pancreas Arms*

- Participants may be contacted between visits if needed, per the discretion of either the participant, a healthcare provider, or a member of the study team.
- Participants using the iLet will not be allowed to travel outside the United States or its territories for the entire time the system is in use.
- Participants may perform calibrations of the Dexcom G6 CGM if it is inaccurate relative to a BG measurement, per the device manufacturer's instructions.
- The iLet will have CGM glucose alarm settings available to the participants. Study staff will work with participants to configure the alarm settings in a way that will be most appropriate for each individual.
 - Study staff will recommend a low CGM glucose alarm be set for 75 mg/dl and a high CGM glucose alarm be set for > 300 mg/dl for 90 minutes.
- If participants receive a high or low CGM glucose alarm, they will be trained to verify the CGM glucose with a fingerstick glucose value using the Contour Next One glucometer.
 - The participant will be trained to treat hypoglycemia with rapid acting carbohydrates, in case the glucometer confirms hypoglycemia. This may be done according to their usual practice or with less carbohydrate than their usual practice since the BP system will typically have suspended insulin delivery prior to the occurrence of hypoglycemia. They will be trained to continue to monitor their glucose levels until they return to normoglycemia.

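### The paired iLet-versus-usual-care tests ignore the randomised sequence, so a chance uneven split in small cohorts would mix any period effect into the secondary difference; possible carry-over is a separate limitation that no re-analysis removes

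*Combined protocol and SAP*

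**What the plan says.** Every participant has one 14-day iLet arm and one 14-day usual-care arm in random order. Section 5.5.3 says that "participants within each of these cohorts will be randomized to one of two possible study arm sequences"; it gives no ratio, blocking or other balancing. The second arm need not wait. For in-person visits (5.6.1.3), "This may occur immediately, or within 14 days after the completion of the first arm"; for telehealth visits (5.6.2.3), "This may occur on the same day, or within 14 days of the final visit of the first arm".

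For iLet against usual care within groups, 6.7 states: "We will use the paired t-test for comparison of means for normally distributed outcomes and the Wilcoxon Signed Rank test". Questionnaire scores are compared by the Wilcoxon signed-rank test. No period term, sequence term, by-sequence table or carry-over check is planned.

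The primary endpoint does not use this contrast: "We will estimate the percentage of participants who have a mean sensor glucose <183 mg/dl in the iLet arms of all four groups". The iLet-minus-usual-care difference belongs to secondary objective 1 (2.2), which seeks preliminary data to power a larger study and expects a larger difference in primary care (PC) than in endocrinology (EN). On testing, 6.7 adds: "P-values can be displayed to aid interpretation, not for inference".

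**The concern.** A paired test treats each within-person difference as an estimate of the treatment effect. In a crossover that difference also contains the period effect, with opposite signs in the two sequences. The two cancel only if the sequences are equal in number. With about 10 people per cohort and no balancing stated, equality is left to chance. What is at stake is the size and the SD of the difference handed to the larger trial, and the PC-versus-EN comparison of differences.

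A second matter is carry-over. Dropping days 1-2 allows for insulin clearance, at least in part, but not for learning. Someone who uses the iLet first has had 14 days of visible CGM and a device about which 1.3.2 says "the iLet continually provides daily insulin dosing recommendations". Usual care may then begin the same day.

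**Working it through.** The plan gives no power calculation (6.6), so there is no figure to reproduce.

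**Inputs from the documents.** About 10 per cohort and 20 per site (5.1). From the adult Bridging Study (Table 2): mean CGM glucose 155 ± 13 mg/dl on the iLet (lispro/aspart) and 163 ± 26 under usual care, a difference of -8.

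**Assumptions, not in the documents.** Period shift of 5-10 mg/dl; carry-over of 5-15 mg/dl; within-person correlation 0.5; simple (unblocked) randomisation for the imbalance probabilities.

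**Model.** Let d = iLet minus usual care, τ the treatment effect, π the period effect (second minus first) and λ the carry-over from the iLet into a following usual-care arm.
- iLet first: E(d) = τ − π − λ
- Usual care first: E(d) = τ + π
- Paired mean: τ + π(n_UCfirst − n_iLetfirst)/n − λ·n_iLetfirst/n
- Average of the two sequence means (period-adjusted): τ − λ/2

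**Period, uneven split.** With π = -10 and iLet first in the majority, the paired mean is off by:

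| Split | Shift (mg/dl) |
|---|---|
| 5:5 | 0 |
| 6:4 | +2 |
| 7:3 | -10 × (3 − 7)/10 = +4 |
| 8:2 | +6 |

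With π = -5 each is halved. The period-adjusted estimate has no shift in any row.

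**How likely an uneven split is, if unblocked.**
- n = 10, 7:3 or worse: 2 × (1 + 10 + 45 + 120)/1024 = 0.344. Exact balance: 252/1024 = 0.246.
- At least one of four cohorts at 7:3 or worse: 1 − 0.656⁴ = 0.81.
- n = 20, 14:6 or worse: 0.115.

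The expected imbalance over randomisations is zero.

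**Period, balanced split (precision only).** SD of d = √(13² + 26² − 2 × 0.5 × 13 × 26) = √507 = 22.5. An unremoved π of 10 raises it to about √(507 + 100) = 24.6. At n = 10 the paired 95% half-width is then 2.262 × 24.6/√10 = 17.6. The period-adjusted one is 2.306 × 22.5/√10 = 16.4 (8 degrees of freedom instead of 9). With no period effect the paired half-width would be 16.1, so adjusting costs about 0.3 mg/dl.

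**Carry-over.** With balanced sequences both analyses are off by −λ/2: +2.5, +5.0 and +7.5 mg/dl for λ = -5, -10 and -15. Simulation at λ = -10 gave a bias of 5.0 for the paired and the adjusted estimate alike. At 7:3 with iLet first in the majority, the paired mean takes 0.7λ and the adjusted estimate still λ/2.

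**What a check can show.** The usual-care-first difference alone estimates τ + π, so it cannot separate carry-over from period. Comparing participants' two-arm totals between sequences isolates λ, but the SD of a total is √(845 + 338) = 34.4, giving a standard error of 34.4 × √(1/5 + 1/5) = 21.8 mg/dl per cohort and 34.4 × √(1/10 + 1/10) = 15.4 per site. First-period data alone avoid carry-over, with a standard error of √(13²/5 + 26²/5) = 13.0 against 22.5/√10 = 7.1 for the crossover. None of these would reliably detect 5-15 mg/dl.

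**The case against.** The case for leaving the plan alone is fair in several respects. This is an unpowered feasibility trial, its primary endpoint is an iLet-arm proportion, and its p-values are declared non-inferential. Silence on blocking does not show that the lists are unbalanced. The PC-versus-EN hypothesis concerns groups of 20, where severe imbalance is less likely than in cohorts of 10. All of this stands and limits the weight of the point. It does not remove it, because the estimate and its SD, rather than a p-value, are what pass to the larger trial.

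A reader might infer more than the documents support:

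- *That the paired tests are biased by period effects as such.* They are not: the bias is zero with balanced sequences and zero on average over randomisation.
- *That a crossover model would cure carry-over.* It leaves the same half of λ.
- *That carry-over occurs, mainly in PC, and so works against the hypothesised pattern.* PC participants are pump-naive and some may be new to CGM, so this is plausible. But PC eligibility does not require CGM naivety, and no figure is given. Section 1.3.2 says the dose recommendations are for temporary self-management if the device is unavailable. A provider helps participants resume usual care (5.6.1.3, 5.6.2.3), and CGM in usual care is blinded for PC non-users (5.4.2). If the inference were right, it would shrink the PC difference, so it could not create a false finding that PC exceeds EN.
- *That 3.2 item 4b contradicts 5.7.1.* Section 5.7.1 says "The UC arm will continue its pre-study diabetes management, including approach to insulin delivery and management" and bars adjustments by the study team. Item 4b only says that dose changes do not count as a planned regimen change. Ordinary self-adjustment fits both.

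**Conclusion.** The point holds as a modest, inexpensive improvement to secondary estimates. The planned tests discard the randomised sequence. If a cohort splits 7:3, the iLet-minus-usual-care difference absorbs 0.4 times the period difference: 4 mg/dl for an assumed 10 mg/dl shift, against 8 mg/dl in the Bridging Study. That benchmark is only a rough scale, since the study used 7-day arms and mixed 12 MDI with 22 pump users. The 34% and 12% probabilities apply only if randomisation is unblocked. If sequences are balanced, the loss is precision alone.

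Carry-over is a possible limitation of the design, not a demonstrated bias and not a consequence of the choice of test. Its size is unknown, and the trial is too small to measure it usefully.

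**What to change.** 1. In 6.7, analyse iLet against usual care as a two-period crossover with treatment and period effects; equivalently, report the average of the two sequence-specific mean differences with its confidence interval. For non-normal outcomes and questionnaire scores, replace the signed-rank test with a rank-sum comparison of the within-person period differences between sequences.
2. In 5.5.3, randomise sequence in blocks within each of the four cohorts. Keep the period term even so, because withdrawals after randomisation (anticipated in 4.1) can unbalance a blocked list.
3. Tabulate iLet and usual-care results by sequence, for glycaemic outcomes and questionnaires, labelled as descriptive.
4. Record changes in the usual-care regimen from that collected at screening (5.2). Section 6.5 lists usual-care insulin doses for EN only, whereas the Protocol Summary also lists self-reported PC doses; reconcile the two so that PC changes are visible.
5. State, wherever the difference is used to plan the larger trial, that no washout was required and that carry-over would bias it by about half its size.

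Cost: wording in the SAP and randomisation specification, some extra regimen data, and no added visits or participants. The statistical price is one degree of freedom. If a cohort still splits 7:3, the standard error is somewhat larger: 0.5 × 22.5 × √(1/7 + 1/3) = 7.8 against 7.1 mg/dl. The by-sequence estimates will be imprecise.
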